5.4.6 Debriefing

Explain whether and how subjects will be debriefed after participation in the study. If subjects will not be debriefed, provide a justification for not doing so. Add any debriefing materials to the study in CATS IRB.

N/A

5.5 Informed consent will not be obtained – request to completely waive the informed consent requirement

Review "HRP-410-Checklist -Waiver or Alteration of Consent Process" to ensure that you have provided sufficient information.

5.5.1 Indicate why the research could not practicably be carried out without the waiver of consent

N/A

5.5.2 Describe why the research involves no more than minimal risk to subjects.

N/A

5.5.3 Describe why the alteration/omission will not adversely affect the rights and welfare of subjects.

N/A

5.5.4 If the research involves using identifiable private information or identifiable biospecimens, describe why the research could not be practicably be carried out without using such information or biospecimens in an identifiable format.

N/A

5.5.5 Additional pertinent information after participation

Explain if subjects will be provided with additional pertinent information after participation. If not applicable, indicate "not applicable."

N/A

- 5.6 Consent Other Considerations
 - 5.6.1 Non-English-Speaking Subjects

Indicate what language(s) other than English are understood by prospective subjects or representatives.

If subjects who do not speak English will be enrolled, describe the process to ensure that the oral and written information provided to those subjects will be in that language. Indicate the language that will be used by those obtaining consent.

Indicate whether the consent process will be documented in writing with the long form of the consent documentation or with the short form of the consent documentation. Review "HRP-091 –SOP- Written Documentation of Consent" and "HRP-103 -Investigator Manual" to ensure that you have provided sufficient information.

Because the surveys used as metrics are not validated for use in non-English-speaking patients, patients who do not speak or read English as a primary language will not be enrolled.

5.6.2 Cognitively Impaired Adults

Refer "HRP-417 -CHECKLIST- Cognitively Impaired Adults" for information about research involving cognitively impaired adults as subjects.

5.6.2.1 Capability of Providing Consent

Describe the process to determine whether an individual is capable of consent.

N/A

5.6.2.2 Adults Unable to Consent

Describe whether and how informed consent will be obtained from the legally authorized representative. Describe who will be allowed to provide informed consent. Describe the process used to determine these individual's authority to consent to research.

For research conducted in the state of Pennsylvania, review "HRP-013 -SOP- Legally Authorized Representatives, Children and Guardians" to be aware of which individuals in the state of Pennsylvania meet the definition of "legally authorized representative."

For research conducted outside of the state of Pennsylvania, provide information that describes which individuals are authorized under applicable law to consent on behalf of a prospective subject to their participation in the procedure(s) involved in this research. One method of obtaining this information is to have a legal counsel or authority review your protocol along with the definition of "children" in "HRP-013 - SOP- Legally Authorized Representatives, Children, and Guardians."

N/A

5.6.2.3 Assent of Adults Unable to Consent

Describe the process for assent of the subjects. Indicate whether assent will be required of all, some or none of the subjects. If some, indicate which subjects will be required to assent and which will not.

If assent will not be obtained from some or all subjects, provide an explanation of why not.

Describe whether assent of the subjects will be documented and the process to document assent. The IRB allows the person obtaining assent to document assent

on the consent document and does not routinely require assent documents and does not routinely require subjects to sign assent documents.

N/A

5.6.3 Subjects who are not yet adults (infants, children, teenagers)

5.6.3.1 Parental Permission

Describe whether and how parental permission will be obtained. If permission will be obtained from individuals other than parents, describe who will be allowed to provide permission. Describe the process used to determine these individual's authority to consent to each child's general medical care.

For research conducted in the state of Pennsylvania, review "HRP-013-SOP- Legally Authorized Representatives, Children and Guardians" to be aware of which individuals in the state of Pennsylvania meet the definition of "children."

For research conducted outside of the state of Pennsylvania, provide information that describes which persons have not attained the legal age for consent to treatments or procedures involved in the research, under the applicable law of the jurisdiction in which research will be conducted. One method of obtaining this information is to have a legal counsel or authority review your protocol along with the definition of "children" in "HRP-013-SOP- Legally Authorized Representatives, Children, and Guardians."

Parental permission and assent will be sought at the same time from minor participants and their parents. The minor will be asked to sign, indicating their assent to participate in this project, as well as their parent will be asked to provide consent. If either party does not wish to sign or does not wish to participate in this study, they will not be enrolled and they will receive standard care in PHP.

5.6.3.2 Assent of subjects who are not yet adults

Indicate whether assent will be obtained from all, some, or none of the children. If assent will be obtained from some children, indicate which children will be required to assent. When assent of children is obtained describe whether and how it will be documented.

All potential participants between 13 and 18 years of age will be asked to provide written assent at time of recruitment into the study, as discussed above. As discussed above, if the child does not (or cannot) provide written assent they will not be recruited, regardless of the parents' desire vis-à-vis this study. Potential participants and their parent(s) will be asked to provide written consent and assent at the same time, as above, and the consent form also includes a specific portion for written assent.

6.0 HIPAA Research Authorization and/or Waiver or Alteration of Authorization

This section is about the access, use or disclosure of Protected Health Information (PHI). PHI is individually identifiable health information (i.e., health information containing one or more 18 identifiers) that is transmitted or maintained in any form or medium by a Covered Entity or its Business Associate. A Covered Entity is a health plan, a health care clearinghouse or health care provider who transmits health information in electronic form. See "HRP-103 -Investigator Manual" for a list of the 18 identifiers.

If requesting a waiver/alteration of HIPAA authorization, complete sections 6.2 and 6.3 in addition to section 6.1. The Privacy Rule permits waivers (or alterations) of authorization if the research meets certain conditions. Include only information that will be accessed with the waiver/alteration.

[Do not type here]

6.1	Authorization and/or Waiver or Alteration of Authorization for the Uses and Disclosures of PHI				
	Check	all that apply: Not applicable, no identifiable protected health information (PHI) is accessed, used or disclosed in this study. [Mark all parts of sections 6.2 and 6.3 as not applicable]			
		Authorization will be obtained and documented as part of the consent process. [If this is the only box checked, mark sections 6.2 and 6.3 as not applicable]			
		Partial waiver is requested for recruitment purposes only (Check this box if patients' medical records will be accessed to determine eligibility before consent/authorization has been obtained). [Complete all parts of sections 6.2 and 6.3]			
		Full waiver is requested for entire research study (e.g., medical record review studies). [Complete all parts of sections 6.2 and 6.3]			

- 6.2 Waiver or Alteration of Authorization for the Uses and Disclosures of PHI
 - 6.2.1 Access, use or disclosure of PHI representing no more than a minimal risk to the privacy of the individual

Alteration is requested to waive requirement for written documentation of authorization

(verbal authorization will be obtained). [Complete all parts of sections 6.2 and 6.3]

6.2.1.1 Plan to protect PHI from improper use or disclosure

Include the following statement as written – DO NOT ALTER OR DELETE unless this section is not applicable because the research does not involve a waiver of authorization. If the section is not applicable, remove the statement and indicate as not applicable.

Information is included in the "Confidentiality, Privacy and Data Management" section of this protocol.

6.2.1.2 Plan to destroy identifiers or a justification for retaining identifiers

Describe the plan to destroy the identifiers at the earliest opportunity consistent with the conduct of the research. Include when and how identifiers will be destroyed. If identifiers will be retained, provide the legal, health or research justification for retaining the identifiers.

All data will be maintained in RedCAP, and will be accessible only to study members. A key linking study participants to study data will be kept for the duration that the study data are kept, and all research data will be retained per FDA regulation and institutional policy. Data maintained in PennState Health drives will be destroyed in accordance with current data management protocols at our institution and paper records will be securely shredded and incinerated.

6.2.2 Explanation for why the research could not practicably be conducted without access to and use of PHI

Provide an explanation for why the research could not practicably be conducted without access to and use of PHI.

Much of the outcomes to be studied here, including weight restoration, length of time in care, or worsening of depression, are assessed on a regular basis as a part of routine clinical care. Because participants in this study will otherwise be undergoing routine care in PHP, access to PHI would reduce need for duplicate visits for study purposes only and should increase study retention. Additionally, certain inclusion and exclusion criteria, such as lab results, will be available in PHI and help determine participant eligibility.

6.2.3 Explanation for why the research could not practicably be conducted without the waiver or alteration of authorization

Provide an explanation for why the research could not practicably be conducted without the waiver or alternation of authorization.

Because participation in this study requires negative urine drug screen and normal bloodwork prior to enrollment, without being able to evaluate PHI prior to enrollment we will not be able to determine who is eligible without duplicating studies and potentially exposing the patient to excessive risk and pain in the form of duplicate lab studies and blood draws.

6.3 Waiver or alteration of authorization statements of agreement

By submitting this study for review with a waiver of authorization, you agree to the following statement – DO NOT ALTER OR DELETE unless this section is not applicable because the research does not involve a waiver or alteration of authorization. If the section is not applicable, remove the statement and indicate as not applicable.

Protected health information obtained as part of this research will not be reused or disclosed to any other person or entity, except as required by law, for authorized oversight of the research study, or for other permitted uses and disclosures according to federal regulations.

The research team will collect only information essential to the study and in accord with the 'Minimum Necessary' standard (information reasonably necessary to accomplish the objectives of the research) per federal regulations.

Access to the information will be limited, to the greatest extent possible, within the research team. All disclosures or releases of identifiable information granted under this waiver will be accounted for and documented.

7.0 Study Design and Procedures

Data collection materials that will be seen or used by subjects in your study must be uploaded to CATS IRB (http://irb.psu.edu). **DO NOT** include any actual data collection materials in this protocol (e.g., actual survey or interview questions)

[Do not type here]

7.1 Study Design

Describe and explain the study design.

This is a double-blind, randomized, placebo-controlled study. We have developed the following schedule of events. All events with a superscript $^{\circ}$ are for study purposes only and are not part of the standard of care:

	Pre-Enrollment Screening: Medical	Enrollment	Week 1	Week 2	Week 3	Week 4	Week 5	Week 6 (end of treatment	Week 8-9 (post- treatment)	Six Months
Intervention								_	>	
Initial Medical Assessment	Х									
Subsequent Medical Assessment, including comprehensive review of systems			x		x		x		х	х
Initial Psychiatry Assessment	X									
Subsequent Psychiatric Assessment, including suicidal ideation			х	х	х	х	х	х	х	х
Discussion of risks and benefits, inclusion and exclusion criteria ^o		х								
Consent/Assent ^o		Х								
\$25 Greenphire Clincardo		Х								х
Urine Drug Screen ^o		Х								
Serum Pregnancy Test (female participants)°		х								
Urine Pregnancy Test (female participants)°					х			х		
Administer Study Article ^o			Х	Х	х	Х	Х	х		
EKG	X									
AST	X				Xº			Xº		
ALT	Х				χ°			Xo		
Total Bilirubin	Х				Xº			Xº		
Direct bilirubin	Х				Xº			Xº		
Heart Rate	Х		Х	Х	Х	Х	Х	Х	Х	Х
BMI	X		Х	Х	Х	Х	Х	X	Х	Х
Height	X		Х	X	X	X	Х	X	X	Х
Weight	X		X	X	X	X	X	X	X	X
Blood Pressure	X		X	X	X	X	X	X	X	X
Temperature Adverse event monitoring ^o	Х		X	x	x	x	x	x	X	X
Suicidal Ideation Screening (ASQ			^	^	^	^	^			
for age <17or C-SSRS for age 18+)		х	Х	Х	х	Х	Х	х	Х	Х
ED-15		Х	х		х			Х	X	х
EDE-Q		Х	х		х			Х	X	Х
ABUSI°		Х	Х		х			Х	Х	Х
GAD-7		Х	х		х			Х	Х	Х
PHQ-9		Х	Х		Х			Х	X	Х
BIS/BAS°		Х	Х		Х			Х	Х	Х

Note: Medical assessments may occur in weeks 1,3 etc or 2,4 etc depending on standard of care for that patient. As long as patients are seen within a 14 day interval (2 week timeframe), the exact week intervals (1,3 or 2,4) may vary. Additionally, the 6 month follow up appointment may take place any time between 5-7 months after study enrollment ends.

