All participants, regardless of sex assigned at birth, gender, or menarchal status, will be required to use a highly reliable form of contraception should they be sexually active. Acceptable options have failure rates of less than 1% and include: combined hormonal contraceptives (such as oral contraceptive pills, patch, or vaginal ring), intrauterine device, depot-medroxyprogesterone injection, etonogesterel-containing implants, and progestin-only contraceptive pills. Condoms, either internal or external, are not sufficient contraception if used alone. If a participant with a birth-assigned sex of female discloses coitus while participating in the study either without the use of contraception or with contraceptive failure (such as a broken condom with no second method of contraception), the participant will be offered a prescription for emergency contraceptive (ulipristal acetate or levonorgesterel 1.5mg) within 72 hours after coitus, pregnancy testing 14 days after the episode of coitus with referral according to results, and will be withdrawn from the study.

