7.1.2 Visit 2 or Day 2 or Post-test, etc. (If applicable)

Provide a description of what procedures will be performed on visit 2 or day 2 or post-test in order of how these will be done. If your study involves more than two sessions or visits replicate this section for each additional session or visit (e.g., 7.2.3, 7.2.4, etc.).

On the first day of study participation after enrollment, all subjects will receive a complete set of vital signs (including heart rate, blood pressure, respiratory rate, temperature, and weight) and urine drug screen including screening for opioid substances prior to receipt of their first dose of study article.

Routine care during PHP for any participant includes every-other-week in-person medical exams for the duration of the patient's stay in program, as well as frequent appointments following completion of PHP, until discharge from clinic. At each medical appointment, patients receive a comprehensive physical exam including complete vital signs as above, and are routinely asked about mood changes, physical changes, difficulty or ease of adhering to routine program protocols, etc. All patients participating in PHP complete routine surveys to assess eating disorder recovery at intake and every three weeks until completion of program. For participants in this study, the documentation of their three- and six-week appointments will be reviewed for evidence of adverse effects related to study participation by study personnel. Participants will also complete two additional surveys, the ABUSI and BIS/BAS, beyond their routine PHP surveys at weeks three, six, and eight/nine. Routine medical testing will be obtained according to clinical need at all medical visits, regardless of participation in this study, for all patients participating in PHP.

For patients participating in this study, liver function panel will be obtained once every 3 weeks at no cost to study participants for the purpose of monitoring drug safety, as well as completion of all of the relevant study indices

The vast majority of patients who require PHP have a routine medical follow-up at approximately six months; for those who do not this appointment will be made at no cost to the participant. At this appointment, participants will again undergo a comprehensive physical

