7.2 Duration of Participation

Describe how long subjects will be involved in this research study. Include the number of sessions and the duration of each session - consider the total number of minutes, hours, days, months, years, etc.

Subjects will be enrolled in this study for a total of six months, starting at enrollment in PHP, and continuing to their final 6-month follow-up visit. They will have study interventions at 0, 3, and 6 weeks, and again at six months. They will take study medication while in PHP, and stop once six weeks of study duration is completed. Duration of PHP is individualized, but is on average about 8 weeks. Duration of PHP will not be dependent upon study participation.

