9.2 Data that are reviewed

Describe the data that are reviewed, including safety data, untoward events, and efficacy data.

Participants in this study will take the study article daily while they are enrolled in program. When they complete program, they will no longer be obliged to take the study article, nor will they be required to have weekly psychiatric evaluation, laboratory evaluation, or suicide assessments. Patients in PHP have at least one medical follow-up appointment two weeks after they complete program, and further follow-up based on the patient's needs.

During the course of the trial, we will monitor:

- New diagnoses of depression, anxiety, suicidal thoughts, suicidal ideation, self-injurious behavior and related diagnoses via chart review. Monitoring for these new diagnoses is a part of routine care of PHP
- The results of every-three-weeks liver function tests
- The results of every-three-weeks urine pregnancy tests in female participants
- Vital signs
- The results of the behavioral health surveys
- New diagnoses of abdominal pain, nausea, vomiting, headache, or fatigue regardless of relationship to diagnosis of eating disorder, though these are common problems in eating disorder treatment
- New diagnoses of jaundice, liver failure, elevated transaminases, rash, or other medical problems that are uncommon in the treatment of eating disorder.
- New diagnosis of pregnancy
- Length of participation in PHP, as patients who are experiencing good results with the study article may require a shortened length of stay in program
- Need for escalation of eating disorder or mental health care, such as need for inpatient
 hospitalization for medical stabilization of eating disorder or other medical diagnosis, need for
 residential care for eating disorder,
- Incidence of death or serious bodily harm
- Incidence of acute withdrawal from narcotic agents (expected to be zero due to preparticipation urine drug screen, though this is a serious event)

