9.3 Method of collection of safety information

Describe the method by which the safety information will be collected (e.g., with case report forms, at study visits, by telephone calls and with subjects).

All patients participating in PHP receive biweekly medical visits, including comprehensive physical exam, vital signs, review of suicidal thoughts or behaviors, review of systems, and review of eating disorder symptom severity and frequency as a part of routine care in PHP. Patients also fill out the Columbia Suicide Severity Rating Scale (C-SSRS a metric assessing for the presence and severity of suicidality) or Ask Suicide Screening Questions (ASQ, a similar metric) once weekly while in care, with patients age 18 and older using the C-SSRS and patients age 13-17 using the ASQ. Participants in this study will be no different, with the notable exception of every-three-week liver function and urine pregnancy tests (assigned female at birth patients only).

Study participants' charts will be reviewed weekly while they are in program by the PI and the study coordinator for any of the above-mentioned possible new diagnoses, lab results, C-SSRS results, as well as review of all routine care detailed above. Study staff who provide direct care to participants will alert the PI and the study coordinator of any adverse events encountered during the course of routine care. The results of all safety screenings will be kept in a comprehensive, secure database and will be reviewed weekly by the study team

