10.0 Risks

List the reasonably foreseeable risks, discomforts, hazards, or inconveniences to the subjects related the subjects' participation in the research. Include as may be useful for the IRB's consideration, a description of the probability, magnitude, duration and reversibility of the risks. Consider all types of risk including physical, psychological, social, legal, and economic risks. Note: Loss of confidentiality is a potential risk when conducting human subject research.

- If applicable, indicate which procedures may have risks to the subjects that are currently unforeseeable.
- If applicable, indicate which procedures may have risks to an embryo or fetus should the subject be or become pregnant.
- If applicable, describe risks to others who are not subjects.

Risks associated with taking oral naltrexone:

- elevated transaminases
- depression and mood changes
- abdominal pain
- nausea
- headache

Additional clinical risks that could be associated with taking Oral Naltrexone:

- Some pediatric autism literature describes low appetite or occasionally worsening of self-injurious behavior while on naltrexone^{8,11,22,22–25,27}. There can also be worsening depression according to the FDA label⁷. These adverse effects are occasionally seen with PHP for eating disorder itself, and therefore we monitor for them frequently as a part of the standard of care. Should the subject or the subject's parent wish to withdraw from the study due to these effects, they are free to do so. If these adverse effects are felt to be related more to the natural history of eating disorder and not to study intervention; or the severity is minor to moderate; the subject may continue to participate in the study if desired. If the effect is severe the subject will be withdrawn.
- Oral naltrexone is a pregnancy category C medication⁷, where there are animal studies that may indicate
 harm to the fetus but no specific human studies on this topic. For this reason, we will test for pregnancy
 in allbirth-assigned females at enrollment using a serum pregnancy screen, and every three weeks
 throughout the study using a urine pregnancy screen. The majority of patients enrolled in child PHP
 have not yet had coitarche, though in adult PHP a history of sexual activity is more common.

Other risks of participation include:

- Loss of confidentiality
- Risk of randomization
- Risk of incidental findings
 Anxiety from completing questionnaires

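### Scheduled pregnancy testing stops in the last dosing week, and open-label naltrexone can start with no pregnancy test required

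*Combined protocol and SAP*

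**What the plan says.** The Section 7.1 schedule has a serum pregnancy test at enrollment and a row headed "Urine Pregnancy Test (female participants" that is marked at weeks 3 and 6. The week 8-9 and six-month cells are empty. Week 6 is labelled the end of treatment, and study article is still marked in that column.

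Other sections describe the testing differently:

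- Section 10 gives possible fetal harm as the reason for testing. It promises a serum test at enrollment and then a three-weekly urine test "throughout the study using a urine pregnancy screen".
- Section 9.2 lists among the monitored data "The results of every-three-weeks urine pregnancy tests in female participants", with no end date. It also says that participants who complete the program are no longer obliged to take study article, "nor will they be required to have weekly psychiatric evaluation, laboratory evaluation, or suicide assessments".
- The Enrollment text (7.1.1) covers a participant who discloses unprotected coitus or contraceptive failure. It offers "pregnancy testing 14 days after the episode of coitus with referral according to results" and withdraws her from the study.
- Section 7.1.2 says of patients in the partial hospitalization program (PHP): "Routine medical testing will be obtained according to clinical need at all medical visits".
- Section 7.3.2 sets up to six weeks of dosing, continued after early discharge from PHP. Afterwards, participants who felt they benefited are offered a naltrexone prescription at follow-up appointments. No pregnancy test is mentioned there.

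**The concern.** The last scheduled test falls while drug is still being taken. A test at that moment cannot be relied on to show a conception from the preceding days, and the schedule has nothing later that would.

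The plan treats pregnancy as a safety matter. Section 9.2 lists a new pregnancy as monitored data, and Section 18.1 counts a congenital anomaly as a serious adverse event. An exposed pregnancy can be followed only if it is found.

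The open-label offer adds a second route to exposure. It depends on perceived benefit and not on treatment arm. A placebo participant could therefore meet naltrexone for the first time, and someone from the naltrexone arm could be exposed again. The week 6 result may be out of date by then.

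**Working it through.** **Inputs**

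- Scheduled tests: serum at enrollment, urine at weeks 3 and 6 (Section 7.1).
- Dosing: six weeks at most (7.3.2), so 6 × 7 = 42 days.
- Participation: six months (7.2 Duration of Participation).
- Sample: 60 participants, 30 per arm (8.1).
- Interval *I* from exposure to an informative test: the plan gives none for scheduled tests. The 14 days comes from the disclosed-episode rule in 7.1.1. The values 7, 10 and 21 days are assumptions that show the range.

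**Step 1: how many three-weekly tests are implied?**

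- Dosing period (to week 6): weeks 3 and 6, so 2 tests. This matches the schedule.
- To the week 8-9 visit: weeks 3, 6 and 9, so 3 tests, one more than scheduled.
- Six months (24 weeks): 24 / 3 = 8 tests, six more than scheduled.

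The liver panel settles how much weight to give this. Section 7.1.2 also describes it as three-weekly, and after screening the schedule marks it at weeks 3 and 6 only. The same phrase used for another safety test thus fits the dosing period.

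**Step 2: what the week 6 test can cover**

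A test on day *T* can reliably find a conception from exposure up to day *T* − *I*. Uncovered dosing days = max(0, 42 − (*T* − *I*)).

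| Test day | *I* (days) | Uncovered dosing days | Share of 42 |
|---|---|---|---|
| 42 | 7 | 7 | 17% |
| 42 | 10 | 10 | 24% |
| 42 | 14 | 14 (days 29-42) | 33% |
| 42 | 21 | 21 | 50% |
| 36 (first day of week 6) | 14 | 42 − 22 = 20 | 48% |

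**Step 3: what a week 8-9 test would add**

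| Test day | *I* (days) | Uncovered dosing days |
|---|---|---|
| 50 (first day of week 8) | 14 | 42 − 36 = 6 (14%) |
| 56 | 14 | 42 − 42 = 0 |
| 56 | 21 | 42 − 35 = 7 (17%) |
| 63 | 21 | 42 − 42 = 0 |

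At 14 days, a test anywhere in the window reduces the gap from 14 days to 6 or fewer.

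**Step 4: earlier stopping**

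The Study Procedures text (7.2) ends study medication at program completion, whereas 7.3.2 continues it to week 6. If dosing stops on day *D* and the day-42 test is still done, uncovered days = max(0, *D* − 28) at 14 days. Day 28 gives 0, and day 35 gives 7 of 35 (20%). The 33% therefore belongs to participants who dose for the full six weeks.

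**Step 5: who could be exposed**

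At most 30 participants receive blinded naltrexone, and fewer once males are removed. The documents give no pregnancy rate, so no expected count can be given.

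**Step 6: first dose against open-label dose**

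Sections 3.2 and 10 require a negative serum test at enrollment. Section 7.3.2 starts naltrexone again, at 25 mg for three days and then 50 mg, with no corresponding requirement.

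**The case against.** A reader might infer that the schedule breaks a clear promise, with six of eight tests missing. The documents do not support that. The liver panel shows that three-weekly can fairly mean weeks 3 and 6, and the week 8-9 column is headed as post-treatment. What stands is a loose phrase that should be tightened.

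A reader might also take 33% as an established monitoring gap. It is not. The 14 days is a management step after a disclosed episode, and the plan nowhere states it as a detection limit. Any last test on the last dosing day leaves some tail.

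There are real safeguards:

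- Sexually active participants must use contraception with a failure rate below 1% (7.1.1).
- Section 4.2.4 calls a pregnancy test for absent or missed menses standard of care for these patients, whether or not they enroll.
- Section 7.1.2 describes frequent appointments after the program. The schedule has medical assessments at week 8-9 and six months, and Section 18.2 has subjects asked about adverse events.
- Section 10 says most patients in the child program are not yet sexually active.

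These make the expected number small, but none assures a test after the last dose. The disclosure rule depends on self-report, and disclosure means withdrawal. The missed-menses test is described under screening. Clinical-need testing is discretionary. The weekly chart check is limited to charts "reviewed weekly while they are in program by the PI and the study coordinator". The program's length ("Duration of PHP is individualized, but is on average about 8 weeks") keeps the average participant under this cover for about 56 days, but someone discharged early and still dosing under 7.3.2 is outside it.

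Finally, the open-label point rests on silence, and a prescriber may well test. It would go too far to say that naltrexone will be prescribed without a test. The supportable statement is that none is required. Nor would a test alone arrange follow-up of a pregnancy's outcome, since Section 3.3.2 provides referral only.

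**Conclusion.** The point holds in a limited form. The difference between Section 10 and the schedule is one of wording and can be resolved by reading the study as the dosing period. Two gaps remain on either reading: the schedule marks no pregnancy test after the last dose, and none is required before open-label naltrexone. The second is the clearer omission, because the plan does require a negative test at enrollment before blinded study article.

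For full six-week dosing with a test on day 42, the uncovered stretch is about 14 of 42 days if 14 days is assumed, and 7 to 21 days across the range shown. It is zero for someone who stops dosing by day 28, again assuming 14 days. Few pregnancies are to be expected, and no count can be derived. No efficacy result is affected. This is a low-cost safety improvement that should be made, and it does not show that the plan is unsafe.

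**What to change.** 1. In 7.3.2, require a negative pregnancy test for birth-assigned females before any open-label naltrexone prescription.
2. In the Section 7.1 schedule, mark a urine pregnancy test for the same group at week 8-9. State a preference for at least 14 days after the last dose (day 56 or later after full dosing), but do not narrow the visit window. The interval is an assumption, and a strict day-56 limit would rule out days 50 to 55, which are most of week 8.
3. Reword Sections 9.2 and 10 to match: serum at enrollment, urine at weeks 3, 6 and 8-9. Make clear in 9.2 that the week 8-9 test remains due after program completion.

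**Cost.** One urine test per birth-assigned female, so at most 60, plus one for each open-label start at a later appointment. The week 8-9 medical assessment is already scheduled. The real burden is a clinic or laboratory visit for anyone who would otherwise complete week 8-9 electronically, as 7.2 Study Procedures allows.
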